Appendix D: Family Survey

(Satisfaction and Acceptability, Oral Health Habits, Experience with Caries and OR, Socio-demographics)

Please mark (X) the best answer to the following questions.

These questions ask about your child's tooth-care	(Select One)
1. How often are your child's teeth brushed?	 2x/day  1x/day  Every other day  Seldom  Never
2. Who brushes your child's teeth? (select all that apply)	 Child Alone  Child with Adult Supervision  Parent/Adult
3. Does your child use toothpaste with fluoride?	 Yes  No  Unsure
4. Does your child use a special high fluoride toothpaste that you can only get by prescription or from your dentist or physician?	 Yes  No  Unsure
5. Other than by our study team, has your child received this school year (or since the last time you filled out this questionnaire 3 months ago) any fluoride painted/put on their teeth by a health care professional (e.g., dentist, hygienist, doctor, nurse, etc.)?	 Yes (Approximately how many times? _____)  No  Unsure
These questions ask about your child's eating habits	(Select One)
6. How often does your child get sugary drinks such as regular soda, sweet tea, chocolate milk, strawberry milk or fruit juice between meals?	 Three or more times a day  One or two times a day  Weekly  Monthly  Never
7. How often does your child get sugary snacks such as raisins, candy, cookies, cakes, or cereal between meals?	 Three or more times a day  One or two times a day  Weekly  Monthly  Never
8. How often does your child typically drink tap water - including filtered water from the refrigerator?	 Daily  Weekly  Monthly  Never
These questions ask about satisfaction with the appearance of your child's teeth	(Select One)
9. How satisfied are you with the appearance of your child's teeth?	 Very satisfied  Mostly satisfied

	 Indifferent or mildly dissatisfied  Quite dissatisfied
10. Does your child find the appearance of their teeth satisfactory?	 Very satisfied  Mostly satisfied  Indifferent or mildly dissatisfied  Quite dissatisfied
These questions ask about satisfaction with the treatment received in this study to treat your child's cavities (select one)	
Questions 11-14 should only be completed after the participant has received SDF/Placebo treatment	
11. Did you find the treatment your child received acceptable (i.e., your child found it OK)	 Yes, definitely  Yes, I think so  No, I do not think so  No, definitely not
12. If a friend had a child with cavities, would you recommend to them the treatment for cavities that your child received as part of this study?	 Yes, definitely  Yes, I think so  No, I do not think so  No, definitely not
13. If one of your children had cavities in the future, would you want him or her to receive the treatment for cavities that your child received as part of this study?	 Yes, definitely  Yes, I think so  No, I do not think so  No, definitely not
14. Considering everything, how satisfied are you with the results of the treatment for your child's cavities received in this study?	 Very satisfied  Mostly satisfied  Indifferent or mildly dissatisfied  Quite dissatisfied
These questions ask about your and your children's teeth	(Select One)
15. Have any of your children had their cavities fixed in the hospital operating room or under general anesthesia?	 Yes  No  N/A
16. Do you have family or friends who have had their children's cavities fixed in the hospital operating room or under general anesthesia?	 Yes  No  Do not know
17. Do you have any of your own teeth? (If Yes, answer Q18. If No, skip to Q19)	 Yes  No
18. Have you had cavities, fillings and/or teeth pulled in the last two years?	 Yes  No
Now tell us a little about you and your child	(Select One; Except #20 and 23)
19. Do you consider your child to be Spanish, Hispanic or Latino?	 Yes  No
20. What is your child's racial background?	 White/Caucasian

(check all that apply)	 African American or Black  Asian  Native Hawaiian or Pacific Islander  American Indian or Alaskan Native  Other (specify) _____
21. Do you primarily speak a language other than English at home?	 Yes  No
22. Do you consider yourself to be Spanish, Hispanic or Latino?	 Yes  No
23. What is your racial background? (check all that apply)	 White/Caucasian  African American or Black  Asian  Native Hawaiian or Pacific Islander  American Indian or Alaskan Native  Other (specify) _____
24. Is an adult in the child's household employed?	 Yes  No
25. Counting you and your child, how many people live with you? (specify a number of children and number of adults counting yourself)	#Children: _____ #Adults: _____
26. Which of the following categories best represents the combined income of all family members in your household for the past 12 months?	 Less than \$5,000  \$5,000 - \$9,999  \$10,000 - \$19,999  \$20,000 - \$29,999  \$30,000 - \$39,999  \$40,000 - \$49,999  \$50,000 - \$79,999  \$80,000 - \$99,999  \$100,000 or more  Don't know

Thank you so much for answering these questions.

Appendix E: Adverse Events

Adverse Event	Mild	Moderate	Severe
Tooth infection (e.g., abscess, fistula, swelling, tooth mobility)	-	Localized; local intervention indicated (e.g., topical antibiotic), or operative/endodontic intervention indicated	IV antibiotic indicated Life-threatening consequences; urgent intervention indicated or Death
Toothache	Mild pain: Over the counter analgesics (e.g., acetaminophen, ibuprofen) indicated	Moderate pain; limiting instrumental ADL; Prescription oral analgesics (e.g., higher potency NSAIDs or low-potency opioids) indicated	Severe pain; limiting self-care ADL; Prescription intravenous analgesics (e.g., mid to high-potency opioids) indicated
Oral mucositis (e.g., erythema, ulceration)	Asymptomatic or mild symptoms; intervention not indicated	Moderate pain; not interfering with oral intake; modified diet indicated	Severe pain; interfering with oral intake
Allergic reaction (e.g., difficulty swallowing or breathing, swelling around the lips or skin of the face, itchiness around the lips or skin of the face, hives or rash)	Transient flushing or rash, drug fever <38 degrees C (<100.4 degrees F); intervention not indicated	Intervention or infusion interruption indicated; responds promptly to symptomatic treatment (e.g., antihistamines, NSAIDS, narcotics); prophylactic medications indicated for <=24 hrs	Prolonged (e.g., not rapidly responsive to symptomatic medication and/or brief interruption of infusion); recurrence of symptoms following initial improvement; hospitalization indicated for clinical sequelae (e.g., renal impairment, pulmonary infiltrates) Life-threatening consequences; urgent intervention indicated or Death
Anaphylaxis	-	-	Symptomatic bronchospasm, with or without urticarial; parenteral intervention indicated; allergy-related edema/angioedema; hypotension Life-threatening consequences; urgent intervention indicated or Death
Vomiting	1 - 2 episodes (separated by 5 minutes) in 24 hrs	3 - 5 episodes (separated by 5 minutes) in 24 hrs	>=6 episodes (separated by 5 minutes) in 24 hrs; tube feeding, TPN or hospitalization indicated
Gastrointestinal pain (e.g., stomachache)	Mild pain	Moderate pain; limiting instrumental ADL	Severe pain with inadequate oral caloric or fluid intake; limiting self-care ADL; tube feeding, TPN, or hospitalization indicated

Diarrhea	Increase of <4 stools per day over baseline; mild increase in ostomy output compared to baseline	Increase of 4 - 6 stools per day over baseline; moderate increase in ostomy output compared to baseline	Increase of >=7 stools per day over baseline; incontinence; hospitalization indicated; severe increase in ostomy output compared to baseline; limiting self-care ADL
Nausea	Loss of appetite without alteration in eating habits	Oral intake decreased without significant weight loss, dehydration or malnutrition	Inadequate oral caloric or fluid intake; tube feeding, TPN, or hospitalization indicated
Extraoral (mucosal) Staining	Staining on skin	-	-
Intraoral (mucosal) Staining	Staining on mucosa	-	-

Based on AE reports for SDF from the literature. Developed from Common Terminology Criteria for Adverse Events, version 4.03, US Department of Health and Human Services, 2010.

Any related AE graded severe will be immediately reported to the Medical Monitor and investigated.

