5.4 Treatment Assignment Procedures

Randomization will be stratified by site. Allocation to SDF/placebo will be 1:1.

5.4.1 *Randomization Procedures*

The randomization schedule will be generated by a biostatistician. Biostatisticians who will be involved in the analyses will remain masked to the trial randomization.

Randomization procedures are explained in more detail in the MOP and the Randomization Plan.

5.4.2 *Masking Procedures*

To ensure concealment of treatment allocation, the identical ampules containing test and placebo product will be assigned sequential identification numbers. The master randomization schedule will not be broken until analyses of the data, or if requested by the DSMB for meetings or due to safety concerns. All trial product will be sealed and labeled as required by the FDA [Section 6.0].

The following steps are being taken to minimize issues associated with bias and masking: 1) Product will be concealed in identical unit-dose ampules, identified by identification numbers, and with liquids of equal color. 2) The trial personnel applying the concealed product at baseline and 6 months will be separate from the trial ICDAS examiner. 3) The parent/guardian, child, and trial caries examiners and trial team involved in any data collection will remain masked regarding trial group allocation. 4) The primary trial outcome (hardness) will be measured independently of the outcome of color (to acknowledge teeth can turn dark, and still remain soft) for all cavitated caries lesions (not only those included and treated in the trial).

5.4.3 *Breaking the Blind*

Randomization code assignment will be broken only under circumstances where participant safety is in question. The participant will be withdrawn from the trial upon breaking of the randomization assignment.

Unmasking of individual subjects' treatment assignments should occur only when knowledge will have a direct bearing on the medical treatment or evaluation of a subject. Whenever possible, the need to unmask should be discussed with the Grant PI and the NIDCR Medical Monitor prior to unmasking. Unmasking procedures are described in more detail in the MOP.

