12.2 Sample Size Considerations

The population will be children 12-71 months of age at the baseline caries examination attending early childhood education programs or recruited from clinics associated with the Michigan, Iowa or New York clinical trial sites. We anticipate 10% attrition over the trial period, as we will follow children over approximately 8 months.

The primary outcome of this trial is the proportion of arrested caries lesions approximately 6 months from the baseline visit (i.e., lesions that have changed from soft to hard over the trial period according to the ICDAS II activity criteria). A 10% difference in the proportion of arrested caries lesions between the SDF and placebo groups will be considered clinically significant. Prior studies in the literature of SDF using this outcome in primary cavitated lesions have shown a wide range for the proportion of arrested caries lesions for both SDF-treated and placebo-treated or untreated lesions; therefore the 10% difference in proportions was calculated assuming 55% versus 45% arrested caries lesions for SDF compared to placebo. In prior studies, an average of 4 lesions was treated per participant, with a within-participant correlation of 0.5; we are conservatively assuming 3 lesions per participant. The sample size calculations used a 2-sided test for a difference in proportions with cluster randomization (participant as the cluster) at significance level $\alpha=0.1\%$, with 80% power to detect a superiority difference of 10% for SDF compared to placebo. The calculations also account for the use of an early stopping rule for efficacy and futility. The interim analysis will be performed after approximately half of the sample has completed the 6-month

examinations. A Lan-Demets spending function with an O'Brien-Fleming type boundary will be used, with p-values for efficacy at 0.000001709 and 0.00099938 at 50% and 100% completion, respectively. Non-binding p-values for stopping due to futility at 50% and 100% completion will be 0.2336928 and 0.00099938, respectively. With the above assumptions, the trial will require 1144 participants to be enrolled. Sample size calculations were made using East version 6.

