Additional GLMs for binary and count outcomes and analysis of covariance models for continuous outcomes, as appropriate for each outcome above, will analyze the effects of covariates and their interactions with the treatment effect.

Aim 4 (Family-level outcomes): The P-CPQ, FIS, and satisfaction and acceptability scores will be compared between the SDF and placebo-treated groups using analysis of covariance, with trial site included as a covariate.

Additional analyses will consider the effects of covariates and their interactions with the treatment effect.

Changes in the color of treated lesions over time will be compared between treatments using a Cochran-Mantel-Haenszel chi-square test, with trial sites as the strata.

The family's experiences with ECC, child's brushing and dietary habits, and color change will be examined as additional covariates for the analyses of satisfaction and acceptability scores.

Safety: The proportion of infected trial teeth at each visit will be compared between the SDF and placebo-treated groups using a generalized estimating equation (GEE) model for binary outcomes, using an exchangeable correlation to account for possible non-independence among multiple teeth within a participant. Trial site will be included as a covariate.

The proportion of participants with adverse events (gum infection, oral mucositis, allergic reaction, anaphylaxis, nausea, vomiting, gastrointestinal pain, diarrhea; individually and the presence of any of the events) during the follow-up period will be compared between the SDF and placebo-treated groups using Cochran-Mantel-Haenszel chi-square tests, with trial sites as the strata.

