During intermediate phone calls, a toothache DDQ score of 1 or higher will trigger the trial team to attempt an unscheduled/emergency clinical visit (Note: we expect these numbers to be low, because during a 6-9 month hospital operating room waiting period in teams' clinics to treat children with S-ECC, only 8-12% of patients required emergency visits due to complaints of toothache pain).

*According to Versloot et al. (2006), 70% of children with cavities and toothache had a DDQ score of 4 or higher, and the average score for these children was 5.73. However, for ethical reasons in this trial, any complaint of toothache pain (DDQ score of 1 or higher) will require an action from the trial team as described above.

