6.12.1. Adverse Events

All reported AEs will be coded using the Medical Dictionary for Regulatory Activities (MedDRA) and summarized by System Organ Class (SOC) and Preferred Term (PT).

Analyses of AEs will be performed for those events that are considered treatment emergent AEs (TEAE), where treatment emergent is defined as: any AE with onset after the administration of study drug (SDF or placebo).

An overall summary of AEs without SOC and PT will be presented with the number and percentage of participants by treatment with any of the following types of AEs:

- TEAE
- TEAE by severity (mild, moderate, severe, life-threatening, fatal)

- TEAE by relationship to study drug (unrelated, related; where unrelated includes not related and unlikely related, and related includes possibly related, probably related, related)
- Serious TEAE
- TEAE leading to study drug discontinuation
- TEAE leading to death

In addition to the overall summary, the number and percentage of participants by treatment for each of the TEAE categories above will be summarized by SOC and PT. In these summaries, each participant will contribute only once to the incidence rate based on the most related occurrence and most severe occurrence of the AE. This is true regardless of the number of occurrences.

Summaries of TEAEs by SOC and PT will also include total number of unique AE occurrences, where unique AE occurrences include all events, regardless of whether the same participant experiences the same AE multiple times. However, if the end of a first occurrence and the start of a subsequent occurrence overlap, or the end of a first occurrence indicates “ongoing”, then this would be counted as only one occurrence.

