9. CHANGES TO PLANNED PROTOCOL ANALYSES

Changes in SAP v3 from the protocol specified analyses include:

- The per protocol population definition was updated.
- Safety population was added.
- A testing strategy for key secondary endpoints was added.
- Safety analyses will be presented descriptively. Formal statistical testing for safety (adverse events) was removed.
- ITT2 and PP2 analysis populations were added (FDA request from pre-NDA meeting)
- Subgroup analyses for efficacy and safety was added (FDA request from pre-NDA meeting)

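### The SAP drops the protocol's category-level adverse event summaries, their composite and the infected-teeth analysis without declaring it, and plans no between-arm difference or interval for safety

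*Protocol*

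**What the plan says.** **Protocol.** Appendix E grades adverse events in clinical categories, several of which hold more than one sign. Oral mucositis covers erythema and ulceration. Allergic reaction covers breathing and swallowing difficulty, facial swelling, itch and skin eruption. The same table has rows for toothache and for "Tooth infection (e.g., abscess, fistula, swelling, tooth mobility").

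Section 12.4 then plans two safety analyses:
- the proportion of participants with gum infection, oral mucositis, allergic reaction, anaphylaxis, nausea, vomiting, gastrointestinal pain or diarrhea, "individually and the presence of any of the events";
- the proportion of infected trial teeth at each visit, by a GEE model.

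Section 12.2 justifies the 24-48 hour safety visit by a 95% upper bound on the SDF-control difference, at most 4 points above the observed difference when events occur in 15% of participants.

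**SAP.** Under 6.12.1, adverse events are "summarized by System Organ Class (SOC) and Preferred Term (PT"). An overall table counts participants with any treatment-emergent event and splits them by severity, relationship, seriousness, discontinuation and death. Each of these is repeated by SOC and PT. The section does not mention Appendix E, the 12.4 list or any grouping of terms. It has no infected-teeth summary, no between-arm difference and no interval.

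SAP 9 says that safety will be descriptive and that "Formal statistical testing for safety (adverse events) was removed".

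**The concern.** Removing a test does not require removing the quantity that was to be tested. The categories, the composite and the infected-teeth proportion could all have stayed as descriptive summaries. A reader of SAP 9 would not learn that they have gone.

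Two features of the replacement tables can make a difference harder to see:
- **Scatter.** The signs of one clinical category may be coded to several preferred terms, and for allergic reaction plausibly to several organ classes. Each row then carries only part of the category.
- **Mixing.** The overall row counts each child once and includes toothache and tooth infection. The protocol hypothesises that SDF reduces pain, and SAP 6.11.1 uses adverse events as one source for identifying early-exit treatment failures. An event can therefore be both an efficacy failure and part of the adverse event count, so fewer such events under SDF would offset more reactions.

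At stake is how clearly the safety summary shows the reactions that the protocol singled out. The primary efficacy result is not affected.

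**Working it through.** **1. The plan's safety precision.** Inputs from the protocol: "the trial will require 1144 participants to be enrolled" and "Allocation to SDF/placebo will be 1:1", so 1144/2 = 572 per arm; "We anticipate 10% attrition over the trial period", so 1144 × 0.9 / 2 ≈ 515 per arm remain; event rate 15% in both arms.

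Half-width = z × √(2 × 0.15 × 0.85 / n).

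| n per arm | one-sided 95% (z = 1.645) | two-sided 95% (z = 1.960) |
|---|---|---|
| 572 | 3.47 points | 4.14 points |
| 515 | 3.66 points | 4.36 points |

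The stated maximum of 4 points is reproduced as a one-sided 95% bound. The protocol figure is sound, but SAP 6.12 plans no output that would deliver it.

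**2. Protocol against SAP.**

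| Protocol 12.4 item | SAP 6.12.1 | Declared in SAP 9? |
|---|---|---|
| Eight categories, one by one | absent; SOC/PT instead | no |
| Composite of the eight | absent; any treatment-emergent event instead | no |
| Infected trial teeth by visit | absent | no |
| Tests between arms for adverse events | absent | yes |

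**3. Dilution in the overall row.** All arm-specific rates here are assumptions, because the documents give none by category for this trial. Take reactions at 15% with placebo (the rate used in Protocol 12.2) and 20% with SDF, 572 per arm. The difference is 5.0 points (95% Wald interval 0.6 to 9.4). Let d be the rate of toothache or tooth infection and r the rate of reactions. If the two are independent within an arm, the rate in the overall row is 1 − (1 − d)(1 − r).

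| d: SDF / placebo | overall: SDF / placebo | difference (95% CI), points |
|---|---|---|
| 12% / 12% | 29.6% / 25.2% | +4.4 (−0.8 to 9.6) |
| 1% / 2% | 20.8% / 16.7% | +4.1 (−0.4 to 8.6) |
| 4% / 8% | 23.2% / 21.8% | +1.4 (−3.4 to 6.2) |
| 6% / 12% | 24.8% / 25.2% | −0.4 (−5.4 to 4.6) |

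For example, in the 1% / 2% row: SDF 1 − 0.99 × 0.80 = 20.8%; placebo 1 − 0.98 × 0.85 = 16.7%.

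The placebo rates of 8% and 12% are the ends of the range in Appendix B, where "only 8-12% of patients required emergency visits due to complaints of toothache pain" during a 6-9 month operating-room wait. Halving under SDF is assumed. SAP 6.11.5 cites the small number of participants with any pain as its reason for not comparing pain episodes or DDQ scores, which makes the 1% / 2% row more credible than the last.

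**4. Scatter over preferred terms.** Assume one category at 10% with SDF and 6% with placebo: +4.0 points (0.9 to 7.1). Spread evenly over four terms (also assumed), each row shows 2.5% against 1.5%: +1.0 point (−0.6 to 2.6). The category row separates the arms and the single-term rows do not.

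**The case against.** A reader might infer that adverse events will appear only as single preferred terms or as any event. The documents do not support that. SAP 6.12.1 also pools by organ class, severity, relationship and seriousness, and organ-class rows are grouped rows in which a child counts once. What remains is that no document maps organ classes to Appendix E.

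A reader might also infer that the SAP hides harm from SDF. That too goes beyond the documents:
- Full masking needs progression rates near the top of an emergency-visit range from another setting, whereas this trial excludes children with toothache at baseline and the SAP reports little pain.
- Lesion pain is compared by arm at 3, 6 and 8 months, so a reader could see an offset in pain forming.
- The tables of related events partly separate product reactions, and the staff judging relationship are masked. They still rest on clinical judgement and pool all event types.

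The division into reactions and progression is not wholly the protocol's. Its 12.4 list includes gum infection, and Section 9.1 names infection among potential adverse reactions to the drug. Restoring the composite as written would not cleanly separate the two. This objection stands and shapes the fix.

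The documents do not show whether sites record events by Appendix E category or by sign. If by category, there is less scatter; if by sign, the fix needs a mapping.

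Finally, the table shells are in a separate document not available here, all eCRF data will be listed, and SAP 6 lets the study report add tables. A category table may therefore exist. However, the shells are to follow the SAP, which specifies none, and groupings chosen after unmasking carry less weight.

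**Conclusion.** The concern holds as an undeclared loss of planned safety summaries, and the SAP should be amended. The missing items are the eight categories, their composite, the infected-teeth summary, and any estimate of the between-arm difference to match the precision in Protocol 12.2. These absences rest on reading the texts side by side, not on assumed rates, with the reservation that the shells were not seen.

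The size of any dilution does rest on assumed rates, independence within arm and 572 children per arm. For a true excess of 5.0 points, the overall row shows between +4.4 and −0.4 points across the cases above. With few pain events it stays close to the true value, at +4.1 in the low-rate case, so the effect is probably modest. The loss from splitting a category depends on how events are coded, which the documents do not show.

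**What to change.** In SAP 6.12.1:
1. Prespecify a mapping from preferred terms to the Appendix E and Protocol 12.4 categories.
2. For each category and for the 12.4 composite, report by arm the number and percentage of participants and the SDF-placebo risk difference with a 95% confidence interval. State whether infection is part of the composite.
3. Show toothache and tooth infection on their own rows, without presuming them unrelated to SDF.
4. Restore a descriptive summary of infected trial teeth by visit and arm.
5. Keep the SOC/PT tables.

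In SAP 9, list the change from the protocol's category, composite and infected-teeth analyses.

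The cost is one additional adverse event table, a short infected-teeth summary and a term mapping. No new data are needed, and formal testing need not return.
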